The overarching goal of the Function QUERI Mentoring Core will be **to** accelerate the adoption of evidence-based practices in VA by training the next generation of investigators focused on implementing and evaluating EBPs to maximize Veterans' function and independence. To meet this goal, the Mentoring Core will recruit outstanding, diverse fellows and junior faculty and provide them opportunities to enhance their knowledge, skills and experience in applying implementation science and working with operations partners and other stakeholders to improve VA health care.

Recruitment and Retention. The Mentoring Core will recruit 2 scholars per year for a 2-year training experience. We will recruit both clinician and non-clinician scientists. Trainees in fellowship programs sponsored by VA's Office of Academic Affiliations (OAA) and other early career VA researchers (e.g. Career Development Awardees) will be eligible to participate. We expect to have high interest in the mentoring program locally; however, for maximum reach, the

program will be non-residential such that trainees at any VA site are eligible to apply. In collaboration with OAA, QUERI, and other university and VA partners, we will advertise and invite applications for our first cohort to begin October 2021. We will recruit via unpaid advertisements, and networking and advertising at appropriate professional meetings (e.g., American Geriatric Society) and social media (e.g., Twitter). Already 7 potential fellows have expressed interest in the program.

Training Opportunity. The Durham VA and Duke University offer a rich environment for implementation science training. Over the last 35 years, Durham's COIN ADAPT has trained 105 clinicians and 38 non-clinician health services research fellows and 27 mentored HSR&D Career Development Awardees. In addition to the OAA health services research fellowship programs, ADAPT is a site for: (1) the National Clinician Scholars Program, a national leadership and research training program for MDs and nurses; and (2) VA Quality Scholars program, an interdisciplinary training program for clinicians focused on health care system improvement. In addition, the COIN ADAPT has had an Implementation Science Methods Lab since 2013. Duke's Department of Population Health Sciences is home to an NIH-funded K12 implementation science fellowship serving 6 scholars. These programs will provide us with a rich pool of candidates for our program and also offer opportunities to leverage existing resources and training experiences. For example, Function QUERI implementation scholars will participate in VA Quality Scholar webinars with topics related to quality improvement, methods and analysis and professional development. Scholars will work with their mentoring team and Core director to develop an individualized training plan. Available opportunities include: (1) didactic courses and webinars; (2) ongoing conferences; and (3) workshop programs.. All components can be attended in-person or remotely. Additionally, Function QUERI will support scholars to attend the annual AcademyHealth Dissemination and Implementation conference for supplemental training and networking opportunities.

Mentored Research Experience. During the 2-year period of training, scholars must acquire both the knowledge and practical skills to perform implementation research, accomplish a body of work significant enough to demonstrate competence as an investigator, and successfully compete for research funds to support implementation or evaluation projects. Scholars will have a primary mentor who is Function QUERI investigator. Supporting mentors can include both Function QUERI investigators and other researchers who have complementary areas of expertise that align with the scholars' training goals. At the start of the fellowship, the mentoring team will work with the scholar to plan a project to be completed within the 2-year period. This could include leadership of a secondary analysis related to one of the EBPs, co-leadership of a Rapid Response project, or leadership on a dissemination product related to implementation core methods or activities. Academic products are important for trainees and therefore we will set a metric that all trainees lead one manuscript during the training period. Additionally, there are many practical challenges and decision points in implementation work that are not common in less pragmatic research. Trainees will therefore participate in all meetings of one EBP or core, so they can experience and play a role in navigating these challenges. Furthermore, it is critical that trainees gain experience in working with operations and regional partners; scholars will participate in Technical Expert Panel (TEP) meetings for hands-on experience in stakeholder engagement and spend one week observing and learning about operations at VISN 6 headquarters, or their home VISN if non-residential. Combined, the program is carefully formulated to supplement scholars' existing and/or ongoing research training with the specialized skills and experience needed to implement and evaluate programs across VA.

Formal Evaluation. Responsible conduct of a training program requires careful monitoring of outcomes across stages and aspects of the program. Therefore, we will evaluate: 1)

Recruitment and selection of fellows, including applications and outcomes for underrepresented minorities and women; 2) Value of training activities from the perspectives of fellows and faculty; 3) The mentored research experience from the perspectives of scholars and mentoring faculty; 4) The record of presentations, peer-reviewed publications and other implementation products from each fellow; and 5) Post-program career experiences, including success in applying for and leading QUERI partnered evaluation projects and other grants, Diffusion of Excellence submissions, implementation science- or quality improvement-focused publications, and other implementation products such as playbooks.

Leadership. The Mentoring Core will be led by [name], Deputy Director of COIN ADAPT and VA Senior Research Career Scientist. [name] is Vice Chair of Education for the Department of Population Health Sciences at Duke University and led ADAPT's OAA fellowship programs for 17 years. He currently leads the NIH K12 Dissemination and Implementation Science in Cardiovascular Outcomes program.

Stakeholder Alignment

Stakeholder engagement is a key underpinning of all Function QUERI activities to promote implementation and sustainment of EBPs. We will work closely with stakeholders through two primary mechanisms: Function QUERI TEP and Durham COIN ADAPT Veterans Research Engagement Panel (VetREP). The Function QUERI TEP includes key VA operations partners, VISN leaders and implementation science experts that align with our EBPs and aims. The TEP members include representatives from 5 different QUERIs, presenting a unique opportunity for cross-pollination of QUERI ideas and best practices. The TEP will convene annually, in person during years 1 and 3 and virtually in years 2 and 4. Meetings will involve discussion of VA national program office and VISN goals related to Function QUERI and how Function QUERI can optimally align with and contribute to those goals and clinical priorities, state of the art in implementation practice and science, review of milestones and presentation of key findings. We will also work closely with VetREP, a robust group that has been active for 3 years and has detailed procedures for member training, monthly meeting structure, and provision of feedback. The panel includes caregivers and Veterans with health conditions and experiences of high relevance to our EBPs. In year 1 we will solicit feedback from VetREP members on all 3 EBPs prior to launch. Thereafter in years 2-4, we will engage VetREP members at least twice annually in discussions relevant to ongoing Function QUERI activities, including dissemination of findings. We will communicate Function QUERI progress to all stakeholders through continued distribution of our quarterly newsletter.

Program Team and Management Plan

The Function QUERI team is comprised of an interdisciplinary group of investigators and clinicians with expertise in all aspects of the proposed program. [name], a geriatrician, is the Corresponding PI for the current Function QUERI program. In her roles as Director of the Durham COIN ADAPT, leader of VISN and GEC supported programs and HSR&D funded clinical trials, she has substantial expertise in leadership of implementation programs, local and national geriatric clinical practice, and partnered research. [name], [name], and [name] will lead Function QUERI's three EBP implementation projects. In addition to project directors, the leadership team is comprised of the Implementation Core ([name], [name]), Rapid Response ([name], [name], [name]) and Mentoring Core ([name]) Directors. Together, the team has the necessary expertise and experience required to successfully accomplish the aims of Function QUERI. Roles and tasks of each member of the investigative team and how the work will be coordinated are described in the Multiple PI plan. We propose a 4-year program of work for Function QUERI.

Risk/Benefit Assessment

There is no prospective patient or caregiver data collection proposed. All patient and caregiver data related to programs will be collected by clinical providers in the course of usual clinical care.

The key informant provider and stakeholder surveys and interviews are minimal risk and focus on organizational readiness, contextual factors and facilitators and barriers to implementation. They do not involve collection of quality of care or personal health information.

Additional Safeguards for Provider Interviews and Surveys. The information gained during the interviews and surveys will not be used to evaluate quality of care. Neither the provider's supervisors nor the provider's peers or patients will have access to the data. Data will remain confidential. No individually identifiable information will be published or disclosed, unless required by law.

In order to protect participants' privacy, we will avoid the use of names during the audiotaped interviews. To protect participants against risk after interview data have been collected, we will take a variety of measures to ensure confidentiality. In all records, participants will be assigned unique identifiers. The key linking unique identifiers to participants, the participation log, as well as all interview recordings and transcripts will be stored electronically in a restricted-use folder on a VA server. Any hard copies of these files will be stored in locked file cabinets in the offices of study personnel.

We will guard against the individual identification of participants in transcripts and research reports by using identifiers and by not identifying specific research sites. These data will be accessible only to the PIs, study staff and the appropriate data management personnel in Durham. The audio recordings to be transcribed will be placed in a dedicated sub-folder of the study's shared folder on the Durham HSR&D Project Drive, and approved Transcription staff, whether internal or external, will access files and complete tasks within this folder. No data will leave the Durham VAHCS. Electronic data will only be stored and accessed through secure VA servers and other VA information systems. Access to primary data will be restricted to those members of the research team with specific need to perform their duties. Data will not be removed from designated VA computer systems, except for archiving at study completion.

Protection of Data from Improper Use or Disclosure

There is a slight risk of breach of privacy resulting from unauthorized use, loss, or disclosures of PHI. However, if such an event occurs, the Durham local site PI and staff

will follow the Durham VA Health Care System's procedures. The lead principal investigator will work closely with the IRB, the ISO, and Privacy Officer if notification to individuals is necessary.

Through their VA training, all staff are familiar with the Durham VA Health Care System's procedure for reporting loss or theft of computer devices, unauthorized use, loss, or disclosures of PHI, or violations of information security requirements is to report the incident immediately (within 1 hour of discovery) to the VA Police, the employee's Supervisor, ISO, and Privacy Officer. Loss or theft of computer devices or PHI will also be reported to the Durham VA IRB as an adverse event.

Benefits. Veterans and caregivers may benefit from participation in the clinical programs (STRIDE, Group PT for Knee OA, Caregivers FIRST) that sites implement. Also, by participating in this project participants are contributing to knowledge that will help the VA better serve Veterans and caregivers in the future.

Selection of Subjects

There is no planned prospective enrollment of, or data collection from, patients or caregivers. Key informants (providers) will be surveyed/interviewed to inform the national implementation and evaluation of the evidence-based practices, deemed a quality improvement effort per certifying letters from national program office partners (see letters in Appendix). They will include members of the site implementation teams as well as organizational leaders (section chiefs, chief of staff, facility director). The selection of patients or caregivers for retrospective data collection in the EHR (implementation and effectiveness outcomes) are as follows below.

Group PT patient sample. Patients will be eligible for the Group PT if they have a clinician diagnosis of symptomatic knee OA. Participants will not be included if they have knee pain from another condition, have substantial fall risk, or have other co-occurring health conditions that would make participation in a group exercise class unsafe. EHR data collection will include program outcomes (adoption, penetration, fidelity) and effectiveness outcomes such as knee function and experience of care (p. 12).

STRIDE patient sample. Clinical criteria for STRIDE participation at each site will include: Age >= 60, admission for medical illness, community-dwelling (i.e. not in a nursing home), not requiring inpatient physical therapy, ability to follow one-step commands and to ambulate safely and independently. EHR data collection will include program outcomes (adoption, penetration, fidelity) and effectiveness outcomes such as length of stay and discharge to nursing home (p. 14).

Caregivers FIRST sample. Targets for participation in Caregivers FIRST are family or friend caregivers of Veterans with functional and/or cognitive impairment, along with

caregivers who have been identified as needing training, education and support (by Caregiver Support Program or others). The target class size for each round of the program is approximately 10-12 caregivers of Veterans, which would yield approximately 20-24 caregivers being trained per 6-month period if the recommended 2 rounds of classes are administered. EHR data collection will include program outcomes (adoption, penetration, fidelity) and effectiveness outcomes such as Veteran days in the community (p. 16-17).

Subject Recruitment

There is no subject recruitment and enrollment for patients, caregivers or providers in this study. As noted above, key informants (providers) at each site will be surveyed and/or interviewed for QI purposes to inform implementation and evaluation of the clinical programs.

Consent Process

N/A

Study Interventions

N/A; observational study

Adverse Events

N/A

Costs and/or Payments to Subjects

N/A

Data and Safety Monitoring

This study carries minimal risk of unexpected or adverse events. The Durham HSR&D Center of Innovation to Accelerate Discovery and Practice Transformation (ADAPT) adheres to VA policy and Durham VAHCS IRB requirements, and also has developed additional Standard Operating Procedures (SOP) for safety monitoring and data security which have been designed to ensure continued confidentiality, integrity, and availability of research data. Privacy or information security incidents will be immediately reported.

With respect to all data, Durham ADAPT SOP procedures mandate the following to ensure confidentiality and safe handling of all data: (1) Access to all participant data and information will be restricted to authorized personnel; (2) Participants will not be identified by name in any reports or publications, nor will data be presented in such a way that the identity of individual participants can be inferred; (3) Each provider participant will be assigned an identifier which will be used on all study forms; and (4) All

study personnel will maintain certification with the Durham VAHCS IRB that they have completed training in research ethics and confidentiality.

With respect to paper-based records, these procedures mandate the following: (1) All study records that contain participant information will be kept in secured locked areas when not in use; and (2) In addition, such materials, when in use, will be kept safe from public scrutiny.

With respect to computer based records, the following practices are followed: (1) All research data are stored on VA-administered servers which are physically secured in a Durham VAHCS server room; (2) Individual computer accounts, password protected, are issued to staff members; and (3) Access to computer data is granted by OI&T personnel after confirming appropriate documentation through the IRB, per ADAPT policies. Utilization and other patient data will be downloaded directly from national files to the Durham HSR&D ADAPT servers or stored in the secure VINCI environment. Of study personnel, only the study Statisticians or other designated personnel will have access to the patient data, which will not be moved from this secured environment.

The key linking the identifiers to the providers' identifying information will be stored in a password protected electronic database and maintained on a password protected VA server, with access only available to approved study staff and investigators.

Withdrawal of Participants

N/A

Data Analysis and Statistical Considerations

The individual projects' sample size determination and analysis plans are as follows below. The data will be analyzed on SAS and SQL local servers (see Location of Data on p. 29) and in the secure VINCI environment by study statisticians and other relevant study team members listed on the IRB-approved study staff listing.

Group PT sample size estimate. Sample size calculations were conducted for the implementation outcomes at 12-months. Using a two-sided t-test based on a sample size of 16 sites (8 foundational REP and 8 enREP), a type-1 error rate of 5%, we will have 80% power to detect an effect size difference of 1.5 and 90% power to detect an effect size difference of 1.7 between arms. For the primary penetration outcome, assuming standard deviations ranging from 1.5 to 2.5 based on data of number of new patients per month over a 1-year period of implementation of Group PT in Durham, these effect size differences correspond to differences in mean number of initiators per month ranging from approximately 2.3 to 3.8 between arms for 80% power and 2.6 to 4.3 for 90% power.

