
Second, we will employ a **qualitatively driven convergent design** (QUAL + *quan*) in which pre-implementation qualitative data are collected at baseline in parallel with quantitative data in order to explore and understand pre-implementation contextual factors related to differences in site-level adoption, addressing the question: *What baseline organizational and implementation team characteristics are associated with sites that don't meet adoption benchmarks?* All projects will use similar approaches to understand organizational readiness to change, organizational resilience, and other common measures. Data sources will include pre-

implementation quantitative surveys and qualitative interviews at baseline to understand organizational and contextual factors and EHR data to define adoption. Key informants will include members of the implementation team as well as organizational leaders (e.g., chief of staff, facility director). In our ongoing Function QUERI work our richest understanding of context has been through qualitative inquiry, and we will use quantitative data collected via surveys administered to site hospital and service-line leadership and EBP implementation team members as an added dimension for understanding qualitative findings. ^{41,46} In order to increase survey participation, we may offer incentives such as an entry into a raffle for small prizes.

Common measures. Consistent with our framework (Fig. 2) we assert that team factors, environmental context and implementation processes including EBP adaptations are critical factors in influencing implementation outcomes. Our ongoing Function QUERI work has demonstrated heterogeneity in extent of adoption of EBPs designed to promote function and independence. An important component of our proposed work is to explore potential pre-implementation contextual contributors to this heterogeneity. Below we provide an overview of domains and example quantitative measures that will be used across projects. Data from survey measures will be integrated with qualitative data as described above.

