Implementation team processes, functioning and self-organization. Team measures will be collected via pre-implementation baseline survey. These measures will include an assessment of team size and team composition. These measures were also assessed in our prior Function QUERI work and determined to be salient factors in teams' ability to successfully implement the EBPs. Other measures will include organizational culture, technological availability,⁴⁷ and participation in decision making.⁴⁸

Environmental context. We will evaluate environmental context using validated measures that address the following constructs: organizational resilience, ⁴⁹ organizational readiness to change, ⁵⁰ and safety culture. ⁵¹ Organizational resilience is a new area of focus because it emerged as a central factor that was much broader than the role of team processes. Organizational resilience is the capacity of an organization to anticipate, prepare for, respond, and adapt to both incremental changes and sudden disruptions in order to survive and thrive. ⁵² We will assess resilience quantitatively using a validated measure that assesses active problem-solving, team efficacy, confident sense-making, and bricolage. ⁴⁹ Organizational readiness to change addresses organizational members' shared resolve to implement a change (change commitment) and shared belief in their collective capability to make a change (change efficacy). ^{50,53} Survey responses will include a five-point Likert scale (e.g., ranging from 0 = 'not at all confident' or 'don't know', to 4 = 'very confident'). We will perform descriptive statistical analyses to calculate percent, mean and standard deviation for individual measures and scales. The VA REDCap survey platform will be used within the VA firewall to survey key informants, who will be sent a VA email inviting them to participate.

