Analyses. To address the question: Are there differences in implementation outcomes (penetration, fidelity) at 6, 12, or 18 months between arms? We hypothesize that sites randomized to higher intensity strategies will achieve higher penetration and fidelity. As part of our type III effectiveness-implementation hybrid design framework, the primary research question compares differences in implementation outcomes (penetration, fidelity, and adoption) between implementation arms at 12 months. Implementation outcomes are continuous, count, and binary outcomes, and generalized linear models⁷⁵ will be used to examine the effect of high-touch support on implementation outcomes at 12 months. The main predictor of interest will be enhanced (high touch) implementation support vs. foundational (low touch) implementation support, and stratification variables for site complexity (low complexity (2, 3, and no complexity) versus all others) and prior implementation of Caregivers FIRST or not will be included; other facility level covariates for consideration are CSP program quality score and size of CSP program. In secondary analyses, implementation outcomes over a 6-month and 18month period will be assessed and described. We will examine how implementation outcomes change over time using descriptive methods (e.g. plots, descriptive statistics, subgroups). Descriptive statistics for survey measures such as organizational readiness for implementation change will be calculated overall and by randomization arm. We will use the same modeling approach described above to examine the effect of the implementation strategy on survey measures. To address the question: What is the impact on effectiveness outcomes/quality metrics (quality of VA General Caregiver Program, Veteran days in the community) at implementing sites? We will assess the impact of Caregivers FIRST on Veteran days in the

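### The only response coding the protocol shows scores 'don't know' as 0 together with 'not at all confident', so where it is used a readiness score cannot separate lack of knowledge from lack of confidence

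*Combined protocol and SAP*

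**What the plan says.** The passage is in the Implementation Core part of the protocol, under Common measures, Environmental context. After describing organizational readiness, which includes "shared belief in their collective capability to make a change (change efficacy)", the text says "Survey responses will include a five-point Likert scale" and illustrates it with a scale "ranging from 0 = 'not at all confident' or 'don't know', to 4 = 'very confident'". The next sentence reads: "We will perform descriptive statistical analyses to calculate percent, mean and standard deviation for individual measures and scales".

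Two uses of the scores are stated:

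- **Baseline context, all projects.** The qualitatively driven convergent design asks: "What baseline organizational and implementation team characteristics are associated with sites that don't meet adoption benchmarks?" On respondents it says: "Key informants will include members of the implementation team as well as organizational leaders (e.g., chief of staff, facility director)." The survey results supplement the interviews.
- **Arm comparison, Caregivers FIRST.** The Analyses text for Implementation Project 3 plans descriptive statistics for survey measures such as readiness, overall and by arm, and adds: "We will use the same modeling approach described above to examine the effect of the implementation strategy on survey measures." Data Analysis and Statistical Considerations repeats this.

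Nowhere do the documents give 'don't know' its own code, treat it as missing, plan to report its frequency, or plan a sensitivity analysis for it.

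**The concern.** 'Don't know' is not a level of confidence. Scored 0, it takes the floor of a confidence scale and enters the mean and SD as if it were a rating. A low site score could then mean that staff doubt they can make the change, or that those who replied were not close enough to it to judge.

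That matters for both stated uses. Respondents range from implementation team members to facility directors, and Implementation Evaluation itself places such leaders further from daily operations. If they choose 'don't know' more often, a site's score depends partly on who replied. In Caregivers FIRST, contact with facilitators could turn 'don't know' answers into ratings. Part of an arm difference in readiness would then reflect familiarity, and the stored scores could not show how much. Both mechanisms are plausible, but the documents contain no data on either.

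**Working it through.** The documents state no survey mean, 'don't know' rate or power figure that rests on this coding, so there is no figure of the plan to reproduce. The check is algebra with assumed inputs.

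**Inputs.** From the documents: a 0–4 scale, 'don't know' scored 0, and means and SDs planned. Assumed: p, the share answering 'don't know' (5–30%); m, the mean among those who give a rating (2.0–3.0); s, the SD among them (1.0 in the table); t, the true mean confidence of the 'don't know' group.

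**Step 1: shift against leaving those answers out.** The coded mean is (1 − p) × m, and the mean with 'don't know' left out is m. The shift is −p × m, which is never upward. The coded SD is √[(1 − p)(s² + m²) − ((1 − p)m)²]. For m = 2.5 and s = 1.0:

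| p | Coded mean | Shift | Coded SD |
|---|---|---|---|
| 5% | 2.375 | −0.125 | 1.117 |
| 10% | 2.25 | −0.25 | 1.209 |
| 20% | 2.00 | −0.50 | 1.342 |
| 30% | 1.75 | −0.75 | 1.419 |

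Over the whole assumed range the shift runs from −0.05 × 2.0 = −0.10 to −0.30 × 3.0 = −0.90 points.

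**Step 2: is the shift a bias?** The true mean of everyone surveyed is (1 − p)m + p × t.

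- Scoring 0 errs by (1 − p)m − [(1 − p)m + p × t] = −p × t.
- Leaving out errs by m − [(1 − p)m + p × t] = p(m − t).

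With p = 20%, m = 2.5 and t = 1, scoring 0 errs by −0.20 and leaving out errs by 0.20 × 1.5 = +0.30. With t = 0, scoring 0 has no error. With t = 2, it errs by −0.40, against +0.10 for leaving out. Scoring 0 is the closer of the two whenever t is below m/2. Neither rule is right without knowing t.

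**Step 3: differences between sites or arms.** Suppose confidence among raters is the same in two groups, with 20% 'don't know' in one and 5% in the other. The coded means differ by (0.95 − 0.80) × m: 0.30 for m = 2.0, 0.375 for m = 2.5 and 0.45 for m = 3.0. If the rates are equal, a difference d among raters becomes (1 − p) × d: it shrinks, and none is created. At p = 20%, for example, a difference of 0.50 becomes 0.40.

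**The case against.** The scale is introduced as an illustration, in a section described as an overview with example measures. A reader might infer that the whole staff survey is scored this way. The documents do not support that: they do not say which items, instruments or projects use this anchor, and they give no response options for the national readiness survey that the team will help the Caregiver Support Program to field. The 'or' might also mean that the bottom label varies by item, although 'don't know' would still score 0. This objection stands, and the point is therefore limited to items that use the coding.

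The environmental context measures are called validated. If the combined anchor belongs to an instrument, changing it would depart from that instrument's scoring. The documents do not settle this, which is a reason to keep the 0 scoring as one of the two presentations.

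A reader might also infer that readiness means are biased downward by p × m. That does not follow, because p × m is the shift against leaving the answers out. The bias is p × t, which is zero if those respondents truly have no confidence. Change efficacy is defined as a shared belief, and someone who does not know arguably does not hold it, so a low score is defensible. Leaving the answers out can bias the mean upward.

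Nor do the documents show that the coding creates an arm or site difference. That needs unequal 'don't know' rates, and no rates are given. A move from not knowing to confident could also be a real gain.

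Finally, item percentages are already planned and would show the share at 0. They would not show how much of that share is 'don't know'.

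**Conclusion.** The point holds in a limited form. Where items use the coding shown, the score merges a non-answer with the scale floor, the merged score goes into means and SDs, and in Caregivers FIRST survey measures are modelled by arm. Nothing elsewhere in the plan lets the two answers be told apart.

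Against leaving 'don't know' out, the mean is lower by 0.10 to 0.90 points under the assumed p and m. The error against true confidence is p × t, and its size is unknown because neither p nor t is given. An artefact of 0.30 to 0.45 points between groups requires rates as unequal as the assumed 20% and 5%.

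The consequence is minor. The surveys supplement qualitative findings, and the Caregivers FIRST arm model of survey measures is not the primary question. No primary outcome, adoption benchmark or sample size uses these scores.

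**What to change.** 1. State which items and projects use the combined anchor, whether it belongs to a published instrument, and how the answer is stored.
2. For surveys not yet fielded, store 'don't know' under its own response code in REDCap.
3. Report the frequency of 'don't know' by site, arm and respondent role.
4. Present readiness means, and the Caregivers FIRST arm comparison, twice: with 'don't know' scored 0, which keeps comparability with surveys already done and with any instrument scoring, and with it treated as missing. If the two disagree, say that the result depends on how non-answers are handled.
5. For surveys already collected with a merged option, report the share at 0 by arm and role beside the mean, and state that the two answers cannot be separated.

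The cost is one response option, a scoring sentence and a second set of summaries. Because the survey is given at baseline and again after implementation, splitting the option between rounds would lose some pre/post comparability. The means with 'don't know' scored 0 limit that loss, and the change of format should be reported.
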